5.3. Primary Endpoint Analyses

All primary endpoint analyses will be based on the ITT set, unless specified otherwise. Only selected analyses of selected endpoints will be repeated on the PP set, as will be indicated.

5.3.1. For Panels 1 and 2

5.3.1.1. Definition of Endpoint

The primary endpoint for Panels 1 and 2 is defined as the change in the proportion of HBsAg+ hepatocytes between baseline and on-treatment Week 40.

5.3.1.2. Analysis Methods

5.3.1.2.1. Missing Data Handling Rule

The primary rule to handle missing data is to use complete-case analysis, i.e., participants must have both baseline and Week 40 biopsy assessments with non-missing number of evaluated hepatocytes and HBsAg+ hepatocytes at both visits.

5.3.1.2.2. Primary Analysis of the Primary Endpoint

5.3.1.2.2.1. Overall Analysis

The change from baseline in proportion of HBsAg+ hepatocytes at Week 40 will be estimated overall – pooling Panels 1 and 2 – by modelling the proportion of HBsAg+ hepatocytes using a binomial mixed model with normal random effects to account for potential overdispersion (Kassahun et al 2012). The potential for overdispersion is supported by preliminary off-treatment results on chronic hepatitis B donors (Sources: Commercial biospecimen sources from Avaden Biospecimen and BioIVT as well as from a pilot phase of phase 0 study NOPRODHPB0012; hereafter referred to as the “donors data”).

The binomial mixed model will model the number of HBsAg+ hepatocytes for each participant at each time point as follows:

$$\begin{aligned}
 Y_{ij} &\sim \text{Binomial}(N_{ij}, p_{ij}) \\
 \text{logit}(p_{ij}) &= \underbrace{(\alpha + \xi_i)}_{\text{intercept}} + \underbrace{(\beta + \gamma_i)j}_{\text{slope}} \\
 &\text{for subject } i = 1, \dots, n \text{ and} \\
 &\text{visit } j = 0 \text{ (for baseline) or } 1 \text{ (for Week 40)} \\
 \xi_1, \dots, \xi_n &\stackrel{\text{iid}}{\sim} N(0, \text{SD}_{\text{intercept}}) \\
 \gamma_1, \dots, \gamma_n &\stackrel{\text{iid}}{\sim} N(0, \text{SD}_{\text{slope}})
 \end{aligned}$$

with:

- Y_{ij} : number of HBsAg+ hepatocytes of subject i at visit j
- N_{ij} : total number of hepatocytes sampled from subject i at visit j
- p_{ij} : probability of a hepatocyte being HBsAg+ for subject i at visit j
- α : Fixed intercept (baseline log-odds of a hepatocyte being HBsAg+) for a “typical” subject, i.e., a subject whose random intercept and slope both equal 0
- ξ_i : Subject-specific random effect for overdispersion of the intercept
- β : Fixed slope (change in the log-odds from baseline to Week 40) for a “typical” subject

- γ_i : Subject-specific random effect for overdispersion of the slope
- n : total number of patients

The input data for this model are Y_{ij} , N_{ij} , and n . There are four parameters to estimate: α , β , $SD_{\text{intercept}}$, and SD_{slope} .

Estimates of the absolute and relative changes from baseline in the proportion of HBsAg+ hepatocytes at Week 40 and associated 80% CIs will be obtained from the model as follows. Let p_0 and p_1 be the proportion of infected hepatocytes at times 0 (baseline) and 1 (Week 40) for a “typical” subject. Based on the binomial model, $p_0 = \text{expit}(\alpha)$ and $p_1 = \text{expit}(\alpha + \beta)$, where $\text{expit}(x) = \exp(x)/[1 + \exp(x)]$ is the inverse of the logit function. The absolute and relative changes from baseline are therefore

- Absolute change: $p_1 - p_0 = \text{expit}(\alpha + \beta) - \text{expit}(\alpha)$
- Relative change: $\frac{p_1 - p_0}{p_0} = \frac{p_1}{p_0} - 1 = \frac{\text{expit}(\alpha + \beta)}{\text{expit}(\alpha)} - 1$

SAS code to fit the binomial mixed model and estimate the quantities of interest is provided in [Attachment 3](#). We may also report estimates and CIs for p_0 and p_1 .

Additional models may be evaluated depending on the distribution of data (such as Poisson, Negative-Binomial or Zero-Inflated regression models) and comparison of fit statistics would be performed to select the most adequate model. Additional covariates may be added to the model based on clinical considerations.

All biopsy data will be used for this analysis, including data collected after treatment discontinuation or occurrence of major protocol deviations ([Appendix 4](#)) potentially affecting the primary endpoint (see [Attachment 2](#)).

5.3.1.2.2.2. Comparison Between Panels 1 and 2

Study panel will be included as an additional covariate in the model described in Section [5.3.1.2.2.1](#). That is, the model for $\text{logit}(p_{ij})$ will become

$$\text{logit}(p_{ij}) = \underbrace{[\alpha + \delta_\alpha I(\text{panel}_i = 1) + \xi_i]}_{\text{intercept}} + \underbrace{[\beta + \delta_\beta I(\text{panel}_i = 1) + \gamma_i] j}_{\text{slope}}$$

with:

- α : Fixed intercept for a “typical” Panel 2 subject
- δ_α : Fixed difference in intercepts (Panel 1 minus Panel 2) for “typical” subjects
- β : Fixed slope for a “typical” Panel 2 subject
- δ_β : Fixed difference in slopes (Panel 1 minus Panel 2) for “typical” subjects
- panel_i : Panel number (1 or 2) for subject i

All other aspects of the model are unchanged from the specification in Section [5.3.1.2.2.1](#).

The input data for this model are Y_{ij} , N_{ij} , panel_{*i*}, and *n*. There are six parameters to estimate: α , δ_α , β , δ_β , SD_{intercept}, and SD_{slope}.

Estimates of the absolute and relative changes from baseline in the proportions of HBsAg⁺ hepatocytes at Week 40 will be provided for both Panels 1 and 2. The between-panel differences (Panel 1 minus Panel 2) in absolute and relative changes will also be estimated. Each estimate will be accompanied by an 80% CI. The estimates can be obtained from the binomial model as follows. Let p_0 and p_1 be the proportion of infected hepatocytes at times 0 (baseline) and 1 (Week 40) for a “typical” Panel 1 subject, and let q_0 and q_1 be defined analogously for a “typical” Panel 2 subject. Based on the binomial model, we have the following relations:

$$\begin{aligned} q_0 &= \text{expit}(\alpha) \\ q_1 &= \text{expit}(\alpha + \beta) \\ p_0 &= \text{expit}(\alpha + \delta_\alpha) \\ p_1 &= \text{expit}((\alpha + \delta_\alpha) + (\beta + \delta_\beta)) \end{aligned}$$

From this we can obtain within-panel contrasts for the absolute change from baseline ($p_1 - p_0$ and $q_1 - q_0$) and the relative change ($\frac{p_1 - p_0}{p_0}$ and $\frac{q_1 - q_0}{q_0}$). The between-panel contrasts of interest are then

- Difference (Panel 1 minus 2) in absolute change: $(p_1 - p_0) - (q_1 - q_0)$
- Difference (Panel 1 minus 2) in relative change: $\left(\frac{p_1 - p_0}{p_0}\right) - \left(\frac{q_1 - q_0}{q_0}\right)$

SAS code to fit the binomial mixed model and estimate the quantities of interest is provided in [Attachment 3](#). We may also report estimates and CIs for p_0 , p_1 , q_0 , and q_1 .

All biopsy data will be used and only complete cases will be considered, similarly to the approach chosen for the primary analysis.

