### 9.2. Sample Size Determination

This study aims to enroll 18 to 24 participants in total across Panels 1 and 2, ie, 8 to 12 participants per study panel.

Due to the exploratory nature of the study, the sample size was determined based on clinical and feasibility considerations related to the liver biopsy procedures performed multiple times during the study, rather than a formal statistical calculation. Nevertheless, a sample size of 8 to 12 participants each in Panel 1 and 2 is considered sufficient to provide adequate precision of the estimate of the primary endpoint (change from baseline to Week 40 in the proportion of HBsAg-positive hepatocytes) as estimated by the 80% confidence interval (CI).

For the estimation of the absolute change in the proportion of HBsAg-positive hepatocytes from baseline to Week 40 for the overall study population (Panels 1 and 2 combined), the following assumptions were made. Assuming an absolute reduction of 70% in Panel 1 (75% at baseline

versus 5% at Week 40) and 29% in Panel 2 (30% at baseline versus to 1% at Week 40), and assuming an inter-subject variability of the change equal to 0.5 on the logit scale in both panels, a binomial model including visit as covariate with normal random effects provides an expected width of the 80% CI of 16.7% for N 24, a width of 17.9% for N 20, and a width of 20.3% for N 16. The point estimates (two-sided 80% CI) are 50.8% (42.5%; 59.1%) with N 24, 50.7% (41.8%; 59.7%) with N 20, and 50.6% (40.5%; 60.8%) with N 16.

For the between-panel difference in the absolute reduction in the proportion of HBsAg-positive hepatocytes from baseline to Week 40 using the binomial model described above augmented with panel as an additional covariate and the same inter-subject variability, the estimated width of the two-sided 80% CI around the difference (Panel 1 – Panel 2) is 17.6% for N 24 (12 per panel), 19.3% for N 20 (10 per panel), and 21.2% for N 16 (8 per panel). The point estimates (80% CI) are 40.4% (31.5%; 49.2%) for N 24, 39.2% (29.6%; 48.9%) for N 20, and 39.4% (28.8%; 50.0%) for N 16.

In addition, N 20 would also be sufficient to provide adequate precision for a between-panel difference in the relative change from baseline of at least 26% in case of large inter-subject variability.

Assuming a drop rate of 20%, the sample size will be therefore set to 12 participants per panel for Panels 1 and 2.

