1.2. Study Design

A target of 24 chronic HBV-infected male and female participants, 18-65 years (inclusive) of age

will be enrolled in Panels 1 and 2, approximately 12 participants in each panel. In Panel 3, a target of 4-6 chronic HBV-infected male and female participants will be enrolled.

- Panel 1 will consist of participants who are HBeAg positive and not currently treated.
- Panel 2 will consist of participants who are HBeAg negative and virologically suppressed by ETV, TD, or TAF treatment.
- Panel 3 will consist of participants who are HBeAg positive or negative and are either not currently treated or virologically suppressed by ETV or TD treatment.

The study will be conducted in 3 phases for all participants:

- A **screening phase** (4 to 6 weeks),
- An **open-label study intervention phase** (48 weeks),
- A **follow-up phase** (48 weeks). Note that the follow-up period will be extended up to an additional 24 weeks for participants who are receiving optional treatment with PegIFN- α 2a and who meet NA treatment completion criteria at the end of treatment with NA and PegIFN- α 2a to ensure all participants have at least one year of follow-up after NA treatment cessation.

The duration of individual participation will be up to 102 weeks for participants who stop NA treatment at the end of the open-label phase, or up to 126 weeks for participants who stop NA treatment during the follow-up phase.

Prior to Protocol Amendment 5, in Panels 1 and 2, participants were randomized in a 1:1 ratio within each panel to receive one of the following interventions (i.e., treatments) for 48 weeks:

- **Arm 1**, combination regimen JNJ-3989+JNJ-6379+NA:
 - 200 mg JNJ-3989 (SC injection Q4W, with the last injection at Week 44), and
 - 250 mg JNJ-6379 (tablets qd), and
 - NA: ETV, TD, or TAF (tablets qd)
- **Arm 2**, combination regimen JNJ-3989+NA:
 - 200 mg JNJ-3989 (SC injection Q4W, with the last injection at Week 44), and
 - NA: ETV, TD, or TAF (tablets qd).

As of Protocol Amendment 5, in Panels 1 and 2, participants who were previously randomized to Arm 1 had to stop JNJ-6379 treatment immediately but will still receive JNJ-3989 and NA – effectively joining Arm 2. New participants will enroll without randomization to Arm 2.

No participants were enrolled in Panel 3 before Protocol Amendment 5 was in effect. Therefore, all Panel 3 participants will enroll without randomization to receive the Arm 2 regimen.

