3. SAMPLE SIZE DETERMINATION

This study aims to enroll 18 to 24 participants in total across Panels 1 and 2, i.e., 8 to 12 participants per study panel. In Panel 3, approximately 4-6 participants will be enrolled.

Regarding Panels 1 and 2, due to the exploratory nature of the study, the sample size was determined based on clinical and feasibility considerations related to the liver biopsy procedures performed multiple times during the study, rather than a formal statistical calculation. Nevertheless, a sample size of 8 to 12 participants each in Panel 1 and 2 is considered sufficient to provide adequate precision of the estimate of the primary endpoint (change from baseline to Week 40 in the proportion of HBsAg+ hepatocytes) as estimated by the 80% confidence interval (CI).

For the estimation of the absolute change in the proportion of HBsAg+ hepatocytes from baseline to Week 40 for the overall study population (Panels 1 and 2 combined), the following assumptions were made. Assuming an absolute reduction of 70% in Panel 1 (75% at baseline versus 5% at Week 40) and 29% in Panel 2 (30% at baseline versus 1% at Week 40), and assuming an inter-subject variability of the change equal to 0.5 on the logit scale in both panels, a binomial model ([Kassahun et al 2012](#)) including visit as covariate with normal random effects provides an expected width of the 80% CI of 16.7% for N=24, a width of 17.9% for N=20, and a width of 20.3% for N=16. The point estimates (two-sided 80% CI) are 50.8% (42.5%; 59.1%) with N=24, 50.7% (41.8%; 59.7%) with N=20, and 50.6% (40.5%; 60.8%) with N=16.

For the between-panel difference in the absolute reduction in the proportion of HBsAg+ hepatocytes from baseline to Week 40 using the binomial model described above augmented with panel as an additional covariate and the same inter-subject variability, the estimated width of the two-sided 80% CI around the difference (Panel 1 – Panel 2) is 17.6% for N=24 (12 per panel), 19.3% for N=20 (10 per panel), and 21.2% for N=16 (8 per panel). The point estimates (80% CI) are 40.4% (31.5%; 49.2%) for N=24, 39.2% (29.6%; 48.9) for N=20, and 39.4% (28.8%; 50.0%) for N=16.

In addition, N=20 would also be sufficient to provide adequate precision for a between-panel difference in the relative change from baseline of at least 26% in case of large inter-subject variability.

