Within each scenario, we set the percent of HBsAg+ hepatocytes at baseline and Week 40 for both Panels 1 and 2. From these four numbers (highlighted in **bold**), the remaining numbers in the table are derived. Data were simulated for each scenario using various sample sizes (assuming an equal number of subjects in each panel) and various values of SD_{slope} (standard deviation for the inter-subject random slope).

The true inter-subject variability of the intercept, $SD_{\text{intercept}}$, where $\xi_i \sim N(0, SD_{\text{intercept}})$, was set to 1.0 across all simulations based on the inter-subject differences observed from the donors data.

In contrast, inter-subject differences in the slopes are unknown, so a range of values of SD_{slope} were considered.

The number of HBsAg⁺ hepatocytes for subject i at visit j , denoted Y_{ij} , was simulated as $Y_{ij} \sim \text{Binomial}(N_{ij}, p_{ij})$, where N_{ij} is the total number of hepatocytes sampled during a biopsy. Based on the donors data, we simulated $\log(N_{i0}) \sim N(10, 0.35)$ for the baseline biopsy, and then $\log(N_{i1}) \sim N(\log(N_{i0}), 0.1)$ for the Week 40 biopsy; values of N_{i0} and N_{i1} were then rounded to integers.

Statistical Analysis of the Simulated Data

For each simulated dataset, we fit both the overall model as specified in Section 5.3.1.2.2.1 and the between-panel model as specified in Section 5.3.1.2.2.2. From the overall model, we estimated the absolute and relative reductions from baseline in the overall proportion of HBsAg⁺ hepatocytes. From the between-panel model, we estimated the between-panel differences in the reductions. For each estimate we obtained an 80% confidence interval (CI). Note that, for ease of interpretation, we present the changes from baseline as “reductions” – simply the negative of changes – so that most of the reported numbers are positive. I.e., a change from 75% to 5% is reported as an absolute reduction of 70% rather than as an absolute change of -70%.

We averaged all the estimates across 1000 simulations. The primary metric of interest is the width of the 80% CIs, which tell us how precisely we can estimate the reductions of interest given the sample size and the assumptions of the data-generating model.

Simulation Results

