ATTACHMENT 3. SAS CODE TO FIT BINOMIAL MIXED MODELS

SAS (version 9.4) PROC NLMIXED may be used to fit the binomial mixed models specified in Sections 5.3.1.2.2.1 and 5.3.1.2.2.2. The advantage of NLMIXED over PROC GLIMMIX – which can also fit binomial mixed models – lies in the power of NLMIXED's ESTIMATE statement, which can conveniently estimate non-linear functions of model parameters. In particular, this allows for convenient estimation of both point estimates and confidence intervals for the absolute and relative changes from baseline and the between-panel differences in the changes.

For the overall analysis in Section 5.3.1.2.2.1, code similar to the following may be used, where the input dataset `insight` should have variables named `id`, `time`, `y`, and `N`.

```
%macro expit(x);
  (exp(&x) / (1 + exp(&x)))
%mend;

ods output AdditionalEstimates=estimates; * save ESTIMATE statement output;
proc nlmixed data=insight alpha=0.2;
  parms a b 0 SD_int SD_slope 0.5; * initialize parameters;

  * specify binomial model with random effects;
  intercept = a + RE_int;
  slope = b + RE_slope;
  logit_p = intercept + slope*time;
  p = %expit(logit_p);
  random RE_int RE_slope ~ normal([0,0],[SD_int**2,0,SD_slope**2]) subject=id;
  model y ~ binomial(N,p);

  * estimate proportions and the change in proportions;
  p0 = %expit(a);
  p1 = %expit(a+b);
  estimate "(1) p0" 100*p0;
  estimate "(2) p1" 100*p1;
  estimate "(3) Abs. change (p1-p0)" 100*(p1 - p0);
  estimate "(4) Rel. change (p1-p0)/p0" 100*(p1/p0 - 1);
run;
```

For the between-panel analysis in Section 5.3.1.2.2.2, code similar to the following may be used, where the input dataset `insight` should have variables named `id`, `time`, `panel`, `y`, and `N`.

```
ods output AdditionalEstimates=estimates; * save ESTIMATE statement output;
proc nlmixed data=insight alpha=0.2;
  parms a delta_a b delta_b 0 SD_int SD_slope 0.5; * initialize parameters;

  * specify binomial model with random effects;
  intercept = a + delta_a*(panel = 1) + RE_int;
  slope = b + delta_b*(panel = 1) + RE_slope;
  logit_p = intercept + slope*time;
  p = %expit(logit_p);
  random RE_int RE_slope ~ normal([0,0],[SD_int**2,0,SD_slope**2]) subject=id;
  model y ~ binomial(N,p);

  * estimate proportions, changes in proportions, and differences in changes;
  q0 = %expit(a);
  q1 = %expit(a+b);
```

```
p0 = %expit(a+delta_a);
p1 = %expit(a+delta_a + b+delta_b);

estimate "(A1) Panel 1: p0" 100*p0;

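### The overall primary analysis pools Panels 1 and 2 without a panel term, so its nominal 80% interval for the absolute change covers 83–94% when panel sizes are fixed, and its relative change is not the overall value in Table 10

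*SAP*

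**What the plan says.** SAP 5.3.1.2.2.1 states that the change at Week 40 "will be estimated overall – pooling Panels 1 and 2 – by modelling the proportion of HBsAg+ hepatocytes using a binomial mixed model". The model has four parameters: a fixed intercept, a fixed slope and two random-effect SDs. The Attachment 3 code agrees: the intercept line is "intercept = a + RE_int", with no panel indicator. Absolute and relative changes are evaluated at the fixed effects, that is, for a typical subject.

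Panel enters only in the next section, 5.3.1.2.2.2: "Study panel will be included as an additional covariate in the model". The overall section also says "Additional covariates may be added to the model based on clinical considerations", but does not name panel.

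Panel sizes are a design choice. SAP 1.2 says participants "will be enrolled in Panels 1 and 2, approximately 12 participants in each panel", SAP 3 sets 12 per panel, and the Attachment 1 simulations use two panels of equal size.

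The stated precision comes from the pooled model. SAP 3 says it "provides an expected width of the 80% CI of 16.7% for N=24", and Protocol 9.2 repeats an "expected width of the 80% CI of 16.7% for N 24". In Table 10 of Attachment 1, four percentages per scenario are set and "the remaining numbers in the table are derived", so the overall row is the simple average of the panels.

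**The concern.** The two panels differ by design: untreated HBeAg-positive participants against NA-suppressed HBeAg-negative ones. A model that ignores panel treats this known, fixed difference as random variation between subjects. The standard error then carries panel-mix variation that fixed panel sizes remove from the estimate.

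The study is estimation-only, so the interval is the inference for the overall primary result. Three things are at stake: whether the 80% interval has its stated level, whether the precision quoted in both documents is right, and what the overall figure estimates.

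**Working it through.** **Inputs.** From Attachment 1: Scenario A 75%→5% (Panel 1) and 30%→1% (Panel 2); B 75%→5% and 30%→10%; C 60%→20% and 30%→10%. Within-panel SD of intercept 1.0; SD of slope 0.5, 1.0 or 2.0; 8, 10 or 12 per panel. From Attachment 3: zero intercept–slope covariance and alpha 0.2. Assumed: t quantile on n−2 df (1.321 for 22 df). With about 22,000 hepatocytes per biopsy, binomial noise is negligible.

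**Target, Scenario A.** Mean baseline logit = (1.099 − 0.847)/2 = 0.126, so p0 = 53.1%. Mean Week 40 logit = (−2.944 − 4.595)/2 = −3.770, so p1 = 2.25%. The typical-subject reduction is 50.9 points absolute and 1 − 2.25/53.1 = 95.8% relative.

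**Reproducing the stated width (A, SD of slope 0.5, N=24).**
- Baseline logit gap between panels: 1.946. Population SD of intercept without a panel term: sqrt(1 + 1.946²/4) = 1.40, against 1.0 simulated.
- Expected ML variances with 12 per panel: intercept 22/24 + 1.946²/4 = 1.863; slope (22/24)(0.25) + 0.295²/4 = 0.251.
- Delta-method gradients: p0(1−p0) − p1(1−p1) = 0.2270 for the intercept and 0.0220 for the slope.
- Model SE = sqrt(0.2270²×1.863/24 + 0.0220²×0.251/24) = 6.3 points. Width = 2×1.321×6.33 = 16.7, the SAP's figure.

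**Actual variability with fixed panel sizes.** The gap no longer contributes: sqrt(0.2270²×1.0/24 + 0.0220²×0.25/24) = 4.6 points. A calibrated width is 2×1.321×4.64 ≈ 12.3. The ratio is 6.33/4.64 = 1.36.

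**Simulation of all 27 cells (20,000 runs each).** Overall absolute widths agreed with Table 11 within 0.2 points. Results for the typical-subject absolute change:

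| Scenario | Coverage of nominal 80% CI | Model SE / actual SD | Simulated width, N=24 | Calibrated width, N=24 |
|---|---|---|---|---|
| A | 91% | 1.34–1.37 | 16.6 | 12.2 |
| B | 91–94% | 1.30–1.45 | 14.3 / 14.7 / 16.3 | 9.9 / 10.4 / 12.4 |
| C | 83–86% | 1.01–1.13 | 8.4 / 10.2 / 15.7 | 7.4 / 9.4 / 15.3 |

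Triple entries are for SD of slope 0.5 / 1.0 / 2.0. Full likelihood fits with binomial counts at 12 per panel gave 91.2% (A, 0.5), 91.3% (B, 0.5) and 85.0% (C, 2.0). In B the slope SD is inflated too: sqrt(0.25 + 2.693²/4) = 1.44 against 0.5.

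**Covariance.** The zero intercept–slope covariance is not the cause. Freeing it in B (0.5, N=24) widens the interval from 14.3 to 17.2 and raises coverage from 94% to 97%.

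**Relative change.** Typical-subject targets are 95.8 / 86.6 / 67.9% in A / B / C. Table 10's overall row gives 94.3 / 85.7 / 66.7%; for A, 1 − 3/52.5 = 94.3%. Table 11 reports 95.7 (94.7, 96.7) in A at 12 per panel and SD of slope 0.5, which excludes 94.3, although Attachment 1 says the two tables agree well. The pooled interval covers Table 10's value in 29–66% of runs in A, 84–98% in B and 77–82% in C.

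**A visible symptom.** Attachment 1 takes it as self-evident that between-panel intervals are wider than overall ones. In Scenario B at SD of slope 0.5, Table 11 shows the reverse for the absolute change: 16.7 / 14.8 / 13.8 between panels against 17.6 / 15.8 / 14.3 overall (8 / 10 / 12 per panel).

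**Equal-weight panel average.** With equal panels, the SE of the average is half that of the difference. Table 11 therefore gives widths 17.6/2 = 8.8, 19.3/2 = 9.65 and 21.2/2 = 10.6 for N = 24 / 20 / 16. Simulated coverage is 77–80% in every cell. Of the 16.5 − 8.8 = 7.7 point gap from the re-simulated pooled width, about 4.3 is miscalibration and 3.4 is the change of estimand.

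**The case against.** - **The error is conservative and decides nothing.** True for the absolute change: no hypothesis is tested and sample size rests on feasibility. This limits the severity, but a nominal 80% interval that covers 91% still misstates precision.
- **The result depends on fixed panel sizes.** Also true. If panel mix were random, coverage at N=24 would be 77–78% in A, 70–73% in B and 75–79% in C. But the plan sets the sizes and simulates them as fixed. With 20% random dropout from 12 per panel, coverage is still 82–89%.
- **Table 10's overall row is not the defined target.** The SAP does define the typical-subject quantity, so low coverage of 94.3% is a mismatch of quantities, not a failure of the model. What stands is that the SAP calls both overall and says they agree. The gap matters only in A, about 1.5 points, and even there the N=24 interval just reaches 94.3 at SD of slope 1.0 and includes it at 2.0.
- **The panel model is already planned.** So the panel-specific and between-panel results are sound. No overall estimate is planned from that model, and the optional covariate clause does not prespecify one.
- **Equal weighting is a choice that nearly halves the width after interim data were seen.** This is the strongest point. It is why the pooled figure must stay in the report and the two sources of narrowing be stated.

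**Conclusion.** The concern holds. As written, the overall primary interval for the absolute change does not have its nominal level: coverage is 83–94%, and in the base case the width is 16.7 where about 12 would be calibrated. The effect is small in Scenario C with SD of slope 2.0 (coverage 83%, SE ratio 1.02). The relative change estimates a different quantity from Table 10's overall row in every scenario, materially in A.

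The pooled target also moves with unequal complete cases. In A it shifts from 50.9 to 55.3 with 12 and 8 complete cases in Panels 1 and 2, and to 46.4 with 8 and 12. The equal-weight average stays at 49.5.

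These figures rest on fixed panel sizes, the SAP's own scenarios and t intervals on n−2 df. The point should be fixed but does not threaten the study.

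**What to change.** Take the overall estimate from the panel model of 5.3.1.2.2.2 with prespecified equal weights, as Table 10 implies. Add to the second code block of Attachment 3:

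- `estimate '(D1) Overall abs. change, equal weights' 50*((p1-p0)+(q1-q0));`
- `estimate '(D2) Overall rel. change, equal weights' 100*((p1+q1)/(p0+q0)-1);`

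Keep the pooled estimate as a sensitivity analysis labelled typical subject, and do not free the covariance as a remedy. In SAP 3, and in Protocol 9.2 at its next amendment, give the panel-averaged widths (8.8 / 9.65 / 10.6) beside the pooled ones. In Attachment 1, label Table 10's overall row as the panel average, note that the pooled relative target differs from it in all scenarios, and correct the statement on interval widths.

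**Cost.** A SAP amendment, two code lines and no new data. The SAP Amendment 2 change table shows that interim data have been used, so the change must be dated and justified by the form of the model.

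**Downsides.** The new absolute interval covers 77–80%, at or slightly below nominal. At N=24 the relative interval widens in A (2.0 to about 3.2 at SD of slope 0.5; 5.1 to 8.4 at 2.0). At SD of slope 0.5 it hardly changes in C (10.0 to 10.2) and narrows in B (10.7 to 5.9). The new target is still an average of two typical-subject values, not a mean over subjects.
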